6. STUDY PROCEDURES

Patients enrolled on study will have the following study assessments and procedures performed as described. For a summary of required assessments, please refer to the study calendar in Appendix B.

6.1 Screening and Baseline assessments

A signed, written informed consent must be obtained before any study-specific assessments are initiated. Results from assessments performed prior to written consent as part of a patient's routine diagnostic workup may be used for screening purposes. The following assessments will be obtained at screening, within 28 days prior to beginning study medication:

- Subject demographic information, to include age, ethnicity, and race
- Medical history, including past and current conditions, and past surgical history
- Whether patient has used Hormone Replacement Therapy (HRT), for how many years, and how long ago she stopped.
- Use of chemotherapy, including taxanes or not including taxanes
- Measurement of body weight, height, and Body Mass Index
- Completion of Health Assessment Questionnaire (HAQ-II)

- Grip strength measurement
- Laboratory assessments to include:
 - Calcium level
 - Albumin level
 - Vitamin D level -- serum 25(OH)D
 - FSH, LH, and estradiol levels must be obtained if required as detailed above in 4.1.4 to determine menopausal status. Menopausal status should be interpreted by the treating physician and approved by study chair based on the cutoff values provided by the reporting laboratory.
- Review of all medications taken within 28 days of planned treatment start date
- Study coordinator will educate the patient about the importance of compliance with Aromatase Inhibitor therapy.
- If a Bone Mineral density test has not been completed within 3 months of starting AI therapy, a Bone Mineral Density test must be ordered as a screening assessment, and the test must be completed within 28 days of starting Aromatase Inhibitor therapy

If the above studies are within acceptable parameters as defined by the eligibility criteria, the patient will be randomized to begin either high dose Vitamin D or standard dose Vitamin D, as described in [Section 7](#).

6.2 Follow-up at Week 4

The following assessments should be performed at 4 weeks (28 days) from the start of study medication. To allow for weekends, holidays, etc., study procedures may be completed within a window of +/- 5 business days.

- Laboratory assessments to include a calcium level, 25-hydroxyvitamin D level, and albumin.

6.3 Follow-up at Week 12

- Measurement of body weight and BMI
- Laboratory assessments to include a calcium level, 25-hydroxyvitamin D level, and albumin.
- Patient is to complete the Health Assessment Questionnaire (HAQ-II)
- Study coordinator will perform grip strength measurement, using the Smedley dynamometer, as described in Section 6.8.2 [Grip Strength Measurement](#).
- Record all concomitant medications added and/or changed.
- Assess compliance to aromatase inhibitor therapy, as outlined in Section 6.8.3

- Assess compliance to vitamin D treatment, as outlined in Section 6.10
- Non-serious and serious adverse events should be recorded and graded appropriately as discussed in section 9.6.
- Administration of study medications will continue as described in Section 6.9.

6.4 Follow up at Weeks 24 and 36

- Laboratory assessments to include a calcium level, 25-hydroxyvitamin D level, and albumin.
- Record all concomitant medications added and/or changed.
- Assess compliance to aromatase inhibitor therapy by counting remaining pills in bottle, as per Section 6.8.3
- Assess compliance to vitamin D treatment, as outlined in section 6.10
- Non-serious and serious adverse events should be recorded and graded appropriately as discussed in Section [9.6](#).
- Administration of study medications will continue as described in Section 6.9.

6.5 Follow up at week 52, and End of Treatment Visit

The following assessments should be performed within five to ten business days of the completion of study therapy. End of treatment is defined as Week 52. These assessments should also be performed for patients who discontinue treatment prematurely (unless otherwise noted below).

- Measurement of body weight and BMI
- Laboratory assessments to include calcium level, 25-hydroxyvitamin D, and albumin.
- Patient is to complete the Health Assessment Questionnaire (HAQ-II)
- Grip strength measurement
- Record all concomitant medications added and/or changed.
- Assess compliance to aromatase inhibitor therapy
- Assess compliance to vitamin D and calcium treatment

Non-serious and serious adverse events should be recorded and graded appropriately as discussed in section 9.6.

At this point, patients will have completed study treatment and should proceed with the completion of their adjuvant therapy, as determined by the treating physician. Patients may take Vitamin D at any dosage they wish, at the discretion of the patient and the treating physician.

6.6 Safety Follow-up

6.7 Upon completion of the therapeutic regimen, subjects will be followed for adverse events for a period of 30 days after the last dose of Vitamin D on study. Patients with abnormal laboratory or clinical findings that are believed to be treatment related will be followed until the condition resolves, stabilizes, or until the laboratory values are no longer considered clinically significant. New adverse events that occur during the 30 day follow-up period will only be recorded if the investigator believes there is a reasonable possibility that the adverse event is drug-related. The safety follow-up may be conducted by a phone visit or a clinic visit; if clinically indicated, a clinic visit should be performed along with relevant lab work. Per standard of care and NCCN guidelines, bone density scan will be repeated, at the treating physician's discretion, every 1-2 years while the patient is on AI therapy. Per NNCN guidelines, patient will have DEXA scan every 2 years while on AI therapy, or every year if accelerated bone loss is suspected, or therapeutic intervention applied. Duration of Follow-up

All subjects will be followed for breast cancer recurrence at approximately 6-month intervals from the completion of the study period (52 weeks) to the completion of the five years of adjuvant therapy. Follow-ups may be conducted by phone, email, or clinic visit, and will be discontinued in the event of subject death, recurrence, loss to follow up after at least 3 documented attempts to contact her, or withdrawal of consent.

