8. DOSING DELAYS/DOSE MODIFICATIONS

8.1 Dose Modifications/Delays

For any patient in the study, if 25-hydroxyvitamin D level exceeds 120 ng/mL at any point, the patient will be taken off the study medication. If the 25 (OH)D level is >90 ng/mL, we will hold the vitamin D supplementation for 4 weeks, and then recheck vitamin D level. If it is <70 ng/mL after 4 weeks, the patient may resume vitamin D at 50,000 IU every other week if the patient was on the lead-in phase of the high dose arm. If the patient was on the continuation phase of the high dose arm, she would instead take 1000 IU/day. If the patient was on the standard dose arm, she would take Caltrate-D once every other day. If the 25-hydroxyvitamin D level did not fall to <70 ng/mL after 4 weeks of a drug holiday, then the vitamin D will be held for an additional 4 weeks. At the end of this 8 week period, patients will resume reduced vitamin D dosing as described above if the level has fallen to <70 ng/mL. However, if the level is still ≥70 ng/mL, then the patient will be taken off the study medication.

Similarly, if the calcium level is >11.0 mg/dL at any time during the study, the patient will be taken off the study. If the calcium level is between 10.5 and 11.0 mg/dL, the patient may follow the same vitamin D reduction schedule outlined above in which the vitamin D supplementation is held for 4 weeks, and may only be resumed at half dose if the calcium level is within normal limits, according to reference lab values. If the calcium level has not normalized after 8 weeks of drug holiday, then the patient will be taken off the study medication.

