9.5 Adverse event follow-up

Investigators should follow-up subjects with adverse events until the event has subsided (disappeared) or until the condition has stabilized. Subjects will be followed for adverse events and serious adverse events for 30-days from the last dose of study drug.

During the 30-day follow-up period, new onset, non-serious adverse events should only be recorded if, in the opinion of the investigator, there is a reasonable possibility the event is attributable to the investigational product. All serious adverse events occurring within the 30-day follow-up period must be reported, regardless of suspected causality.

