9.6.3 Serious Adverse Events

Any serious adverse events that occur during the clinical study or within 30 days of receiving the last dose of study medication, whether or not related to the study drug, must be reported by the

investigator. In addition, any SAEs which occur as a result of protocol specific diagnostic procedures or interventions must also be reported.

All serious adverse events must be reported to the PI within 1 business day of becoming aware of the event. The protocol chair will then report SAEs to the Baylor College of Medicine IRB, in accordance with standard operating procedures. Events should be reported using a MedWatch form (FDA Form 3500), which is available for download on the FDA website.

The SAE report should comprise a full, written summary detailing relevant aspects of the adverse events in question. Where applicable, information from relevant hospital case records and autopsy reports should be included. Follow-up information and follow-up reports should be forwarded to all appropriate entities within 24 hours.

Instances of death, if brought to the attention of the investigator AT ANY TIME after cessation of study medication, and linked by the investigator to a previous clinical trial, should be reported to the FDA.

The PI will disseminate information regarding serious adverse events to the participating investigators within 5 days of review of the information by the Protocol Chair (or designee in the event of extended absence) only in the case that the event(s) is believed to be related (i.e., possibly, probably, or definitely) to the study medication.

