APPENDIX B STUDY CALENDAR

Study Procedure	Baseline (- 28 d)	Week 4	Wk 12	W 24	W 36	W 52	EOT	Safety Follow-up ² (+/- 7 d)	Follow-up for recurrence ³ (+/- 30 d)
Informed Consent	X								
Demographics	X								
Medical history	X								
Body weight measurement	X		X	X	X	X	X		
Health Assessment Questionnaire	X		X			X	X		
Grip Strength Measurement	X		X			X	X		
Review concomitant meds	X		X	X	X	X	X		
Bone Mineral Density Test ⁴	X								
Adverse Event Assessment			X	X	X	X	X	X	
Assess compliance ¹			X	X	X	X	X		
Assess disease & vital status									X
Calcium, Albumin, and 25(OH) Vit D levels	X	X	X	X	X	X	X		

1. Compliance assessment as determined by pill count and/or pill diary.
2. A safety follow-up should be performed 30 days after the last dose of study medication, even in the event of early discontinuation. Physical exam and laboratory assessments need only be performed if clinically indicated.
3. Recurrence follow ups will be performed every 6 months for the 4 years following the completion of the 52 week study period.

Study Procedure	Baseline (- 28 d)	Week 4	Wk 12	W 24	W 36	W 52	EOT	Safety Follow-up² (+/- 7 d)	Follow-up for recurrence³ (+/- 30 d)
------------------------	-----------------------------	-------------------------	--------------	-----------------------	-----------------------	-----------------------	------------	--	---

4. The Bone Mineral Density test must be ordered as a screening assessment, and results must be available within 28 days of starting AI therapy. If not completed within 28 days, patient will be taken off trial.

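### Section 6.7 drops unrelated serious events that 9.5, 9.6.3 and 14.1 require, and the 30-day safety window, dated from the last dose, has passed before a woman is stopped after a full 8-week hold

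*Combined protocol and SAP*

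**What the plan says.** **The safety window.** The paragraph numbered 6.7, under the 6.6 Safety Follow-up heading, states that after the regimen is complete "subjects will be followed for adverse events for a period of 30 days after the last dose of Vitamin D on study". Section 9.5 repeats it: "Subjects will be followed for adverse events and serious adverse events for 30-days from the last dose of study drug". Appendix B, footnote 2, dates the visit the same way: "A safety follow-up should be performed 30 days after the last dose of study medication, even in the event of early discontinuation". The calendar column allows 7 days either side.

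**What is recorded in the window.** Section 6.7 limits all new events to those with a reasonable possibility of being drug-related. Section 9.5 applies that limit to non-serious events only and requires all serious ones. Section 14.1 draws the same line. Section 9.6.3 covers serious events during the study or "within 30 days of receiving the last dose of study medication, whether or not related to the study drug, must be reported".

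**The hold.** For 25(OH)D above 90 ng/mL, Section 8.1 says "we will hold the vitamin D supplementation for 4 weeks, and then recheck vitamin D level". If the level has not fallen below 70 ng/mL, "then the vitamin D will be held for an additional 4 weeks". At the end of the 8 weeks, "if the level is still ≥70 ng/mL, then the patient will be taken off the study medication". Calcium between 10.5 and 11.0 mg/dL follows the same holds, with permanent stopping if calcium has not normalized after 8 weeks.

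**Status after stopping.** For these women 8.1 speaks of leaving study medication. Section 6.14 says that participants meeting any 6.12 criterion are removed from the study, and 6.12 lists persistent elevation of 25(OH)D or calcium among its criteria.

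**The concern.** There are two separate problems.

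The first applies to every participant. Four sections describe event recording in the 30 days after treatment, and one of them contradicts the other three on serious events. Section 6.7 is the procedural text that a coordinator would follow for the safety call. Read literally, it tells her not to record a hospitalization judged unrelated, which 9.5, 9.6.3 and 14.1 all require.

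The second applies only to women who go through both holds. Whether a dose was the last one is known only when the decision to stop is made. By then, a window counted from that dose has already closed. Section 9.3 lists kidney stones and arrhythmias among the anticipated effects of high vitamin D. A first occurrence after the stop would fall outside any scheduled collection period if the woman is treated as off study. What is at stake is complete and uniform safety reporting, not the efficacy result.

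**Working it through.** **Serious events in the 30-day period**

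| Section | New non-serious events | New serious events |
|---|---|---|
| 6.7 | only if possibly drug-related | same limit, no exception stated |
| 9.5 | only if possibly drug-related | all, regardless of cause |
| 9.6.3 | not addressed | all, regardless of cause |
| 14.1 | only if possibly drug-related | all, regardless of cause |

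The sections agree on non-serious events wherever they address them. On serious events 6.7 stands alone, and both readings cannot be followed for an unrelated serious event.

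**Timing after a full hold**

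Inputs: window of 30 days from the last dose (6.7, 9.5); contact at day 30 with 7 days either side (Appendix B); first hold of 4 weeks and second hold of 4 weeks (8.1); weekly dosing in the high-dose lead-in phase (6.9.1).

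1. The plan's own figure: 4 + 4 = 8 weeks, as 8.1 states. In days, 28 + 28 = 56.
2. Days from closing of the window to the stop: 56 − 30 = 26.
3. Latest permitted contact: 30 + 7 = day 37. Days from then to the stop: 56 − 37 = 19.
4. These are minimums, because they assume that the hold starts on the day of the last dose. If it starts 0 to 7 days after a weekly dose, the stop falls on day 56 to 63. That is 26 to 33 days past the window and 19 to 26 days past the latest permitted contact. With daily dosing (0 to 1 day), the stop is 26 to 27 days past the window.

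**What is still collected for these women**

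- During the hold: 9.1 and 9.6.3 both cover events on study as well as the 30 days after the last dose. A woman on hold may still resume, so she reads most naturally as on study. Section 14.1 asks about events at weeks 12, 24, 36 and 52.
- At the stop: 6.12 sends women who discontinue early to the 6.5 assessments, which include adverse events. The end-of-treatment column of Appendix B agrees.
- Known abnormalities: 6.7 follows abnormal findings believed to be treatment-related until they resolve, stabilize or cease to be clinically significant.
- New events after the stop: no scheduled 30-day window is dated from the stop. Whether the later inquiries in 14.1 still apply depends on whether 8.1 or 6.14 governs her status. The recurrence follow-up column in Appendix B marks disease and vital status only, not adverse events.

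**The case against.** The strongest case against acting is that the plan has several overlapping safeguards. Events during the hold are collected, the stop itself triggers an assessment, and the abnormal level is followed open-endedly. Section 9.1 also asks participants to report serious post-study events reasonably related to participation, and asks investigators to notify the IRB of unanticipated deaths or events that may be related. All of this stands, and it makes the gap narrow. It does not close it. The 9.1 provision depends on spontaneous reports and on a judgement of relatedness, the open-ended follow-up concerns findings already known, and the 6.5 assessment is a single contact.

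On the causality conflict, one can say that three sections outweigh one and that a careful site would apply the stricter rule. That is probably how an audit would resolve it, but the text leaves the choice to the site.

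Stronger readings are tempting, and the documents do not support them:

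- A reader might infer that adverse event collection simply ends at day 30, or that nothing is due after the stop. Sections 9.1, 9.6.3, 14.1, 6.5 and 6.12 say otherwise.
- A reader might infer that these women's levels never fell. The criterion is a level still at or above 70 ng/mL after 8 weeks, which a falling level can meet.
- A reader might infer that 30 days is too short for women stopped at once above 120 ng/mL. Section 8.1 sets recheck times and gives no expected rate of decline. For these women the last dose and the stop nearly coincide, so the 26-day gap does not arise.
- A reader might infer a safety comparison biased in favour of the high-dose arm. The documents give no expected number of women failing both holds, and 14.1 plans descriptive summaries. No bias can be sized from them.

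**Conclusion.** Both parts hold, and both are minor. Section 6.7 contradicts 9.5, 9.6.3 and 14.1 on serious events in the 30-day period. This is a plain wording conflict that can affect any participant. For women stopped after both holds, the safety contact date has passed by at least 26 days, or at least 19 days with the calendar allowance, and no scheduled 30-day window for new events runs from the stop. Sections 6.14 and 8.1 leave it unclear whether later inquiries continue.

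The timing rests only on date arithmetic, with the assumption that the hold begins on or shortly after the day of the last dose. The number of women affected is not given in the documents and is presumably small. The primary endpoint and the sample size are not affected.

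**What to change.** 1. Amend 6.7 so that serious events in the 30-day period are recorded regardless of causality, as in 9.5, 9.6.3 and 14.1. Keep the causality limit for non-serious events.
2. In 6.7, 9.1, 9.5, 9.6.3, 14.1 and Appendix B footnote 2, end collection at the later of 30 days after the last dose and 30 days after the date of permanent discontinuation. State that events during a hold count as on-study. For a stop on day 56, collection then runs to day 56 + 30 = 86 after the last dose. Women stopped without a hold see almost no change.
3. Reconcile 6.14 with 8.1 on whether a woman stopped after a hold remains in the study and whether the scheduled adverse event inquiries continue.

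The cost is protocol wording plus one later contact for the few women stopped after a full hold. Section 6.7 already allows that contact by phone. Thresholds, holds, doses and stopping rules are unchanged.

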6.8 On Study Assessments and Procedures

6.8.1 Health Assessment Questionnaire

Each subject will be asked to complete the Health Assessment Questionnaire (HAQ-II) at baseline, 12 weeks, and 52 weeks. The questionnaire will be completed in the office, during the clinic visit, and it will be administered by the study coordinator. Generally, the questionnaire can be completed in less than 5 minutes by most patients. The questionnaire will be available in English, Spanish, and Vietnamese.

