3. STUDY DESIGN/SUMMARY

This is a randomized, multi-center, controlled, phase II study comparing high dose vitamin D vs. standard dose vitamin D for post-menopausal breast cancer patients who are beginning adjuvant aromatase inhibitor therapy. The study is intended to be conducted in up to 5 centers within the U.S.A which are routinely engaged in the administration of aromatase inhibitor therapy for the study specified population. All patients who are starting an AI in the adjuvant setting are eligible to participate in the study.

In order to preserve power and compensate for the interim futility analysis which tends to reduce power, the sample size of the study is increased from 88 per group to 93 per group, which is 186 total if considering a 5% drop out rate. A total of 186 patients at up to 5 centers will be randomized 1:1 to receive either 50,000 International Units (IU) oral vitamin D per week for 12 weeks followed by 2000 IU daily for 40 weeks, or 800 IU Vitamin D daily for 52 weeks. All women on both arms of the trial will also take calcium carbonate 600 mg daily.

The primary endpoint for this study is development of AIA in each arm after 12 weeks of AI therapy, as determined by patient questionnaires. Secondary endpoints include compliance with AI therapy, as well as correlation of low baseline vitamin D levels with development of AIA. Grip strength is an exploratory endpoint.

[figure not shown]
Throughout the 52 week study period, participating women will complete the questionnaire and grip strength measurement a total of three times in order to assess their arthralgia while on AI therapy. Compliance with aromatase inhibitor (AI) therapy will also be assessed throughout the

Vitamin D for AIA

study to determine if AI compliance is improved in women who are receiving Vitamin D. Additionally, women will also have periodic assessments of serum 25-hydroxyvitamin D to assess whether vitamin D levels correlate with AIA, and to ensure that calcium and 25(OH) D levels are within healthy ranges.

SCHEMA

High Dose vs. Standard Dose Vitamin D for Aromatase Inhibitor-Induced Arthralgia

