12.1 Definitions

12.1.1 **Evaluable for toxicity:** All patients will be evaluable for toxicity from the time of their first treatment with Vitamin D.

12.1.2 **Evaluable for response:** All the patients who have been randomized will be considered evaluable for response, regardless of how much treatment they have received,

consistent with an intention to treat analysis. These patients will have their response classified according to the definitions stated below. Any patient who began the study medication, but does not complete the HAQ at 12 weeks, will be deemed to be a study failure (i.e. the development of AIA will be assumed), consistent with an intention to treat analysis.

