13.2 Sample Size/Accrual Rate

The primary objective of this study is to determine if supplementation of high dose Vitamin D prevents AIA in women being treated with adjuvant aromatase inhibitors. The Health Assessment Questionnaire II (HAQ-II) will be used to assess joint pain symptoms. Previously published estimates of AIA incidence showed that 33% of women on standard dose of vitamin D, and 19% of women on a high dose of vitamin D, developed AIA (43). Assuming a one-sided test with $\alpha=0.10$, $\beta=0.20$, we would need 93 women in each arm to detect a different rate of AIA development using the Chi-square test. Assuming 5% dropout rate in the first 12 weeks, we will accrue 93 women to each arm, for a total of 186 women. Sample size calculations were conducted using nQuery Advisor 7.0, Statistical Solutions, USA. Given that there are over 8000 office visits each year in our Baylor Clinic and Smith Clinic, we should easily be able to recruit an average of 4-6 women/month to the study, which would allow us to complete accrual in approximately 3 years.

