13.4 Primary Endpoint

Descriptive and summary statistics will be computed for all demographic and clinical data in each treatment group. The HAQ-II will be used to assess joint pain symptoms; a higher score indicates more severe joint pain. Scores will be evaluated for the development of AIA between baseline and Week 12, as well as between baseline and Week 52, though development of AIA at 12 weeks will be the primary endpoint. The scores will be dichotomized as “development of AIA” (as defined above, in Section 12.2) or “no development of AIA.” Group differences in AIA rate will be assessed using the Chi-square test. Development of AIA at week 12 will be used to test the primary objective. The week 52 data will be measured and reported as well. As exploratory analyses, development of AIA will be assessed using logistic regression, adjusting for potential confounders such as age at diagnosis, race/ethnicity, BMI, receipt of chemotherapy, taxane use, and use of hormone replacement therapy. All statistical tests are one-sided with $\alpha = 0.10$ as the level of significance.

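### The week-12 HAQ-II has no back-up route or stated window, yet a treated woman without one is counted as having AIA; the power a back-up would recover lies between 0 and about 6 points

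*Combined protocol and SAP*

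**What the plan says.** Section 6.8.1 schedules the HAQ-II at baseline, week 12 and week 52 and fixes how it is taken: "The questionnaire will be completed in the office, during the clinic visit, and it will be administered by the study coordinator". It gives no telephone, postal or take-home alternative. A tolerance of 5 business days either side appears under week 4 (section 6.2); section 6.3, for week 12, has none, and the study calendar adds none.

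Section 12.1.2 covers women who began study medication but have no week-12 HAQ. They are classed as failures, meaning that "the development of AIA will be assumed". It does not say how randomized women who never started are to be scored.

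Other data have fallbacks. If pill bottles are not brought in, AI compliance is taken by direct questioning (6.8.3). Safety follow-up may be by telephone, and for recurrence: "Follow-ups may be conducted by phone, email, or clinic visit".

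The design assumes that "33% of women on standard dose of vitamin D, and 19% of women on a high dose of vitamin D, developed AIA" (13.2). For the analysis, "Group differences in AIA rate will be assessed using the Chi-square test" (13.4), one-sided at 0.10. Section 13.2 allows for 5% dropout in the first 12 weeks. Section 13.7 sets a non-binding futility look at 46 per group.

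**The concern.** Sections 6.8.1 and 12.1.2 act together. The first narrows the ways a form can be obtained; the second turns an absent form into an event. A woman without joint pain who is travelling or unwell at week 12, and is not rebooked, is recorded as having the outcome the trial is meant to prevent.

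Three things are at stake:

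- Equal missingness in the two arms adds false events to both, shrinks the difference and lowers power.
- It also raises the chance that the interim look recommends stopping when the planned effect is real.
- Unequal missingness biases the comparison itself. The documents describe no placebo or blinding, and the regimens differ visibly (ten capsules once a week against one tablet a day), so unequal attendance cannot be ruled out.

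**Working it through.** **Inputs.** AIA 33% (standard) and 19% (high dose), one-sided alpha 0.10, power 80%, 93 per arm and 5% dropout (13.2); chi-square test (13.4); 1:1 allocation (section 3); futility boundary Z = 0.076 at 46 per group (13.7). The final critical value is 1.2816, the one-sided 0.10 point, which matches the Z of 1.28 in the 13.7 table.

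**The plan's own figure.** With pooled variance and no continuity correction, mean rate 0.26:

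n = [1.2816 × √(2 × 0.26 × 0.74) + 0.8416 × √(0.33 × 0.67 + 0.19 × 0.81)]² / 0.14² = (0.795 + 0.515)² / 0.0196 ≈ 87.6, so 88 per arm. This matches the 88 that section 13.7 raises to 93.

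**Effect of the missing-form rule.** If a fraction m of forms is missing, unrelated to true AIA, and scored as AIA, a true rate p becomes p* = m + (1 − m)p. At m = 5%:

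- standard: 0.05 + 0.95 × 0.33 = 36.35%
- high dose: 0.05 + 0.95 × 0.19 = 23.05%
- difference: 13.3 points instead of 14

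**Exact two-stage power.** All binomial outcomes were enumerated: 46 per arm, stop if Z ≤ 0.076, otherwise add 47 per arm and reject if Z > 1.2816.

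| Missing per arm | Standard / high dose after the rule | Power | Futility stop under planned effect |
|---|---|---|---|
| 0% | 33.00% / 19.00% | 80.0% | 7.6% |
| 2.5% | 34.68% / 21.03% | 77.0% | 8.7% |
| 4% | 35.68% / 22.24% | 75.1% | 9.3% |
| 5% | 36.35% / 23.05% | 73.8% | 9.8% |
| 10% | 39.70% / 27.10% | 67.8% | 11.9% |

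**What a back-up route could recover.** Start from 5% missing. Recovering a share r leaves 5% × (1 − r). The documents do not give r, so the full range is shown:

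- r = 0: no gain
- r = 1/5 (4% left): 75.1 − 73.8 = 1.3 points
- r = 1/2 (2.5% left): 77.0 − 73.8, about 3 points
- r = 1 (none left): 80.0 − 73.8, about 6 points

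**Where the loss comes from.** By the normal approximation without the futility look, power at 93 per arm is 81.8% with complete data, 80.2% if 5% are missing and left out, and 76.1% if they are scored as AIA. About 1.5 points come from fewer observed women and 4.1 from the scoring rule. Under that rule, 80% power would need 106 per arm before any futility adjustment.

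**Unequal missingness (assumed splits, same enumeration).**

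- 8% high dose, 2% standard: 25.48% vs 34.34%, power 49.1%.
- 2% high dose, 8% standard: 20.62% vs 38.36%, power 90.4%.
- The second split with true AIA of 33% in both arms: 34.34% vs 38.36%, false-positive rate 22%, against 9% with nothing missing.

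**The case against.** The strongest reply is that the 5% in section 13.2 is dropout, not missed appointments. A posted form cannot bring back women who withdrew or were lost, so the gain may be close to zero. This stands, and it is why the saving is given as a range starting at 0.

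A reader might infer that any missed appointment at once becomes an arthralgia event. The documents do not say so. The trigger in 12.1.2 is a HAQ never completed, and only in women who began study medication. Rebooking is not barred. Sites have reason to rebook, because week 12 also needs blood tests, grip strength and pill counts, and the high-dose arm changes product then. Early discontinuers are also to complete the HAQ-II (6.5, 6.12). What remains is that no rule says how late a form may be and still count.

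Most of the power loss comes from 12.1.2, not from the office setting. That is correct, and it is a reason to add sensitivity analyses as well as a second route.

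A single supervised setting is a defensible choice. A change of 0.3 on the pain score, 0.3 / 0.2 = 1.5 cm on the 15 cm line, is enough to define AIA, so mode of completion could matter. Permission to take recurrence status by telephone or email is weak precedent for a scored instrument. These points favour keeping the clinic visit as the main route. They do not justify assigning an event without data when the same form could have been posted.

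The futility effect is modest, and the boundary is non-binding.

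**Conclusion.** The point holds as a gap in data capture with a bounded cost. As written, an obtainable week-12 form can be lost and replaced by an assumed event. If 5% per arm are missing, power is 73.8% instead of 80.0%, and the chance of crossing the futility boundary under the planned effect is 9.8% instead of 7.6%. A back-up route recovers between 0 and about 6 of those points.

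These figures assume the plan's 33% and 19%, equal missingness, and missingness unrelated to true AIA. Where a woman stays away because of joint pain, the rule scores her correctly.

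Two stronger readings are not supported. A reader might infer that a take-home form would restore the full 6 points; nothing in the documents gives the recoverable share. A reader might also take 49% power as the likely result of unequal missingness; that split is assumed, and its reverse gives 90% power with an inflated false-positive rate. The supportable conclusion is that unequal missingness biases the result in a direction that cannot be known in advance.

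Severity: minor to moderate.

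**What to change.** 1. In 6.8.1, state a window for the week-12 HAQ-II.
2. Add that, if the visit cannot be held within the window, the woman completes the same pre-printed form at home, dates it and posts it back within that window. The form asks about the past week, so a late return would describe a different period. It should be the printed form, not an emailed copy, so that the pain line keeps its length.
3. In 12.1.2, apply the assumed-AIA rule only when neither route yields a form.
4. Record the route of completion. Repeat the primary test on clinic-completed forms only, as a check on mode of completion, and under alternative handling of the forms still missing (for example, leaving them out), as a check on the rule.

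The cost is postage, one CRF field, a short amendment and two supporting analyses. The downside is a possible small mode-of-completion difference for a few women, which the recorded route allows to be examined.
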